Screening, intervention flow sheets, and consult order sets are currently in EHR-driven workflows of both inpatient nurses and social workers at Rush. Leveraging the EHR infrastructure, the manual screen is driven by four key components: (1) connect the nursing and social work navigators into a single workflow that allows both disciplines to document screening information into a common flowsheet in the EHR; (2) a status column in the unit patient list where the social work team indicates the current stage of the intervention for each patient; (3) a consult order to addiction medicine that operates within a work queue managed by the SUIT team; and (4) a flowsheet for the SUIT team to document the details of the intervention. Specifically, if patients report positive to the

universal manual screen during the rooming process, an indicator in the substance use column updates to signal a social worker to conduct a full manual screening with the Alcohol Use Disorders Identification Test (AUDIT) and/or Drug Abuse Screening Tool (DAST). Once completed, the social worker is guided by a risk-stratified score (Table) and may provide a brief intervention using motivational interviewing. If the score is high risk, the social worker may recommend a consult to the SUIT team for addiction services. The consult team determines with the

Table. Cutoffs to categorize patients into risk zones for substance misuse

	AUDIT Score		Description of Category
	Male	Female	
Zone 1	0	0	No alcohol use
Zone 2	1-7	1-4	Low-risk alcohol use
Zone 3	8-15	5-12	Mild/moderate alcohol use
Zone 4	≥16	≥13	Severe alcohol use*
DAST Score			
Zone 1	0		No drug use
Zone 2	1-2		Low-risk drug use
Zone 3	3-5		Mild drug use
Zone 4	6-8		Moderate drug use
Zone 5	9-10		Severe drug use*

*at-risk for substance use disorder (SUD)

patient whether to initiate medication and linkage to outpatient services upon discharge. If ready, patients may begin medication and, upon discharge, receive individual and group psychotherapy, case management, continued medication treatment at an outpatient addiction medicine clinic. The study coordinator will collect the following elements: (1) documentation and modality of SBIRT was performed by the provider (Yes/No); (2) dose assessed by documentation of brief intervention, motivational interview, or referral to treatment; and (3) reasons for no receipt (e.g., patient refusal).

Clinical decision support (CDS) with substance misuse NLP classifier:

[figure not shown]

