All analytics for the NLP classifier will be performed on Rush Servers by the Rush Addiction Data Science Lab. Linguistic processing of all clinical documents for the NLP classifier is performed in the clinical Text and Knowledge Extraction System version 4.0 (cTAKES) open-source Apache software tool (<https://ctakes.apache.org/>). These include linguistic pre-processing modules for breaking the text into sentences and tokens, and tagging the tokens with parts of speech (e.g., noun, adjective). Next, candidate phrases are matched to a dictionary of concepts, by default SNOMED CT and RxNORM, and tagged with concept codes from the original dictionary, and a Concept Unique Identifier (CUI) from the National Library of Medicine's Universal Medical Language System (UMLS) Metathesaurus. For the concept codes, cTAKES recognizes the words or phrases from the notes as medical terms that represent the domain concepts (named entity mentions) to understand the relations between the identified concepts. The Unified Medical Language System (UMLS) includes over 2 million concepts from nearly 9 million distinct names from 152 sources that are merged into the Metathesaurus. The spans of the UMLS named entity mentions (diseases, symptoms, anatomy, and procedures) will be identified and organized into CUIs. For instance, the named entity mention for '*heroin abuse*' is assigned C0600241 as its CUI. '*Heroin abuse*' is mapped to a separate CUI than 'history of heroin abuse' which is C3266350. The classifier is fed all the CUI predictors/features as inputs into the machine learning model that will serve as the automated screening tool. The software has been developed and is currently available in the Rush Addiction Data Science Lab (led by [name]) at <https://github.com/Rush-SubstanceUse-AILab/SubstanceMisuse>.

Our team will work to integrate the automated screen into the EHR established SUIT as an email alert from the backend data warehouse. Prior to switching on the automated screen, all inpatient nurses and social workers in participating units will be asked to participate in a brief in-service training on the tool and termination of the manual screening program on the day when the automated screener is initiated. Additional emails will be sent to inform providers who could not attend the training session.

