ACFs and partial ACFs will be used to determine the orders of autoregression (AR) or moving average (MA) that will correct for the remaining autocorrelation. We hypothesize that the intervention will promote a step change (binary indicator for a level shift when intervention begins) and possibly a ramp effect (variable takes the value of 0 before the intervention and increases by 1 for each month following the beginning of the intervention). Fit statistics (AIC, BIC) and residual analysis (Ljung-Box test for white noise) will be used to identify a parsimonious and appropriate model based on AR/MA orders, differencing assumptions, and parameters for intervention impact (step, pulse, or ramp).

Specific aim 2: The number of hospitalizations in the 6 months following the index encounter will be regressed on time period of index hospitalization (manual screen or automated screen) and patient demographic and clinical characteristics using mixed-effects Poisson regression models. GLMMs with appropriate link and distributions specified will consider other follow-up utilization outcomes (e.g., costs, any encounter).

Power analysis:

A simulation study was designed to examine potential step effects in a non-inferiority design. In 2020, there were 95 ± 10 addiction consults per month and an autocorrelation AR(1) of $\phi=0.4$. Additionally, we performed silent testing of the automated screener in 2020 where it detected ~ 70 additional cases of substance misuse per month that did not receive consults by the usual care approach. We propose that a non-inferiority margin of 15 consults is acceptable and a step effect of 20 is a feasible goal with the implementation of automated screening. Assuming a similar consult rate of 95 ± 10 per month in this study's pre-period (July 2022-June 2023) and $\phi=0.4$, we have 80% power to detect a step effect of +20, resulting in 115 ± 10 consults per month in the post-period (July 2023-June 2024).

Data Elements:

RUSH EHR

The following electronic health record data elements will be included in the data sets used for analysis. Most data will be obtained through direct extraction of EPIC; however, some data may be computed from EHR data and obtained through the Rush Clinical Research Analytics team or transformed from EHR data by the research team (NLP mapped concepts from the text):

- MRN
- Address with Geocoding
- Census Tract Identifiers
- Encounter ID and type

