- Date / time Stamps for all EHR data (e.g. admission / discharge, procedures, assessments, notes, etc. (time-shifted for final analysis))
- De-identified concept unique identifiers (CUIs) from all clinical documentation in the EHR (process described below)
- Nursing assessments and flowsheets including AUDIT, DAST, and universal screens
- Clinical / nursing assessments, flowsheets, documentation including SUIT data
- Insurance status
- Vital signs (including respirator settings and data)
- Co-morbidities
- ICD and CPT codes

- Cost, charges and reimbursement data associated with all the CPT, ICD9/10, and medications
- patient location
- laboratory results
- radiological orders
- interventional orders including addiction consult orders
- diagnostic test orders
- medication ordered and administered
- sex
- age
- race / ethnicity
- primary and secondary diagnoses
- date of admission
- date of discharge
- dates related to notes, assessments, procedures, orders, reports, vitals, observations, events, diagnoses, etc.
- discharge disposition
- adverse events during hospitalization, defined as Rapid Response Team activations, ICU transfer, cardiac arrest, or mortality
- OR procedures
- OR admission and discharge

DURATION

It is expected that participant enrollment will begin by January 1, 2018 and that human subjects activities will be complete by June 30, 2024. In this pre-post design, a manual screen cohort of patients will provide the comparison. The automated screen period will run prospectively on hospitalized patients over a 12-month period between July 1, 2023 and June 30, 2024. During these study periods, all patient data (for patients ages 18 and above) will be collected.

LOCATION

Research will be conducted at Rush University Medical Center by study staff from Rush. Staff from ITM Loyola and UW-Madison may consult on analyses. All data will be housed at Rush and analyzed on our systems. PHI will not be released outside of Rush.

TYPE AND NUMBER OF SUBJECTS

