This study involves "no more than minimal risk." There are no planned interventions that would pose any significant risk. All of the instruments used in this study have been previously used and studied in psychiatric research studies. The completion of psychiatric diagnostic instruments and psychological assessments can involve the recollection of past symptoms and previous history. Recollection of events always poses some degree of risk in that individuals may experience distress if their past histories are particularly traumatic. The SBIRT program used in the study is currently in place and part of usual care. The program has been well studied in multiple populations, and no adverse events as a consequence of this patient-centered care are foreseeable. Universal screening is already performed on all hospitalized patients so consenting patients is not feasible but the social workers using the universal screen will have the opportunity to opt-out of using the substance misuse classifier. Nevertheless, a data safety and monitoring board (See SAFETY MONITORING section below) has been formed to track and monitor for any unintended consequence of the automated screener as a universal screen for SBIRT.

There is no direct benefit to patients whose electronic health records we will use. However, there is potential future benefit to new patients. The proposed research will provide new screening tools that may be used in patients hospitalized and at-risk for substance misuse. Tools developed with the methodologies we investigate will improve our ability to perform clinical decision support. In addition, creating improved and scalable methodologies for text processing will allow health providers in other domains to access detailed information about patient symptoms, the course of disease onset, diagnosis, treatment, and social history. This previously unavailable knowledge will enable more accurate and complete data on screening for preventable and treatable health conditions.

PLAN TO PROTECT IDENTIFIERS FROM IMPROPER USE AND DISCLOSURE:

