A data safety monitoring board has been established to ensure that the data remain confidential and that the participants are not experiencing any harm from the intervention. A committee to ensure that the plan is followed will be formed. The committee will meet every three to six months during the 24-month study period. Members of the data safety monitoring board will include individuals who have demonstrated expertise in the areas related to the project and have agreed to serve in this capacity. [name], is a Professor and Chair of Public Health Sciences in the School of Medicine at Loyola University Chicago and will serve as the Chair of the Data Safety Monitoring Board (letter of support). He has extensive experience in clinical trials and has extensive experience in health inequities research. He has conducted numerous clinical studies and has more than 20 years of NIH funding. [name], MD, is an Associate Professor at Indiana University and a practicing Hepatologist with several NIH/NIAAA-funded grants examining patients with alcoholic hepatitis. He has performed multiple clinical studies in hospitalized patients and involved in clinical trials for alcohol hepatitis treatment. [name], MD, is an Associate Professor at University of Colorado and a critical care physician and currently the PI of a NIAAA R24 multi-site collaboration collecting patient samples for alcohol research. She is familiar with the potential harms in performing alcohol research in hospitalized patients. Finally, [name], PhD, is a Professor of Biostatistics at University of California San Diego and has served on data safety monitoring boards for clinical trials and will help to evaluate the statistical analyses and reports provided by the study team. Of note, the study team will provide the proportion screened and identified to have substance misuse as one of the important metrics to determine any harm that is being incurred in patients missed for SBIRT by the substance misuse NLP classifier.

The Progress of Study and Safety of Patients:

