The following data will be examined to evaluate safety issues: adverse events and rates of adherence to Screening, Brief Intervention, and Referral to Treatment (SBIRT) at all contact points. In order to provide a level of protection to all patients, the following will be specifically included for monitoring and follow-up: (1) number (if any) of patients who were identified by the care team to have substance misuse but was not captured by the automated screener; (2) number (if any) of patients who received screening but refused any intervention; (3) number (if any) of patients who began medication or were referred for treatment; (4) number (if any) who had withdrawal syndrome. Of note, the risks involved with this study are considered low and the manual screen in the control group is an approved intervention for substance misuse by the United States Preventive Services Task Force (USPSTF), the National Institute of Drug Abuse (NIDA), the Center for Disease Control and Prevention (CDC), and the Substance Abuse and Mental Health Service Administration.

- (1) *Compliance with the reporting of adverse events:* Determining whether all adverse events and/or unanticipated problems were reported in writing to Rush University Medical Center and the IRB within 48 hours of discover of the incident. Priority of the DSMB is to analyze presence of any level of harm to patients.
- (2) *Data Accuracy and Protocol Compliance:* Evaluating records for the training of personnel and other protocol documents as needed. All research staff personnel will be required to have human subjects training, HIPPA training, and training on all study protocols. Drs. [name] and [name] will have weekly lab meetings with the project staff and co-investigators. The Substance Use Intervention Team have already been trained for SBIRT and addiction counseling in their practice of usual care currently in place at Rush. At baseline and every six months thereafter, the following will be done by [name], [name], and the staff to ensure compliance: (1) reviewing study documents; (2) auditing the data collection forms for missing data and reasons for missing data; (3) performing analyses of the performance of the substance misuse classifier to ensure no major deviance and harm is occurring. Priorities of the DSMB are to ensure the accurate reporting of the safety data including: 1) manual and automated screening estimates; 2) screen fails; 3) missing data.

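### The planned count of missed patients covers only those the care team recognised, and no independent reference is named for unflagged patients once manual screening ends

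*Combined protocol and SAP*

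**What the plan says.** - **Safety Monitoring, The Progress of Study and Safety of Patients.** Item (1) for monitoring and follow-up is the "number (if any) of patients who were identified by the care team to have substance misuse but was not captured by the automated screener". Identification by the care team is not defined, and no denominator is given. Item (4) counts withdrawal syndrome, without a split by flag status. The same section plans analyses of classifier performance at baseline and every six months. It also lists manual and automated screening estimates, screen fails and missing data as priorities for the monitoring board. No reference standard is named for any of these.
- **Safety Monitoring, opening paragraph.** On harm to patients whom the classifier misses, "the study team will provide the proportion screened and identified to have substance misuse as one of the important metrics".
- **Clinical decision support.** Staff training covers "termination of the manual screening program on the day when the automated screener is initiated". The classifier's input is described as "Linguistic processing of all clinical documents for the NLP classifier".
- **Potential Risks & Benefits.** Here "the social workers using the universal screen will have the opportunity to opt-out of using the substance misuse classifier", which implies that the universal screen is still in use.
- **Approach.** In the manual workflow, a positive patient-reported universal screen leads to a social-work AUDIT and/or DAST.
- **Power analysis.** The plan states that "we performed silent testing of the automated screener in 2020" and reports about 70 additional cases a month that had no consult under usual care.
- **Data Elements.** AUDIT, DAST and universal-screen flowsheets, concept codes from clinical documents, "laboratory results" and ICD codes are all listed for extraction.

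**The concern.** Replacing one screen with another can harm patients whom the old screen would have found and the new one does not. The board is asked to watch for this. Item (1) looks like the measure for it, but it depends on a clinician having recognised the patient. The Scientific Review section says that provider teams write the substance-use history in their notes, and the classifier reads clinical documents. Recognition and flagging are therefore likely to succeed or fail together.

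The patient-reported screen depends least on provider notes, and it is the one to be switched off. A patient picked up by neither the team nor the classifier would leave no trace in item (1). The primary outcome would not show the loss either: it is a count of patients receiving any component of care, so newly found patients can offset lost ones. The board could read a small number as reassurance when it is an undercount.

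**Working it through.** The plan gives no false-negative figure, so there is none to reproduce. The check is a reading of the text plus illustrations on assumed values.

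**1. What can enter item (1).** Divide true cases in the automated period by whether the care team identified them and whether the classifier flagged them. Item (1) is the cell identified and not flagged. The cell not identified and not flagged is also a miss, and the item never sees it. If the manual program ends at switch-on, the plan names no other source to fill that cell: no concurrent AUDIT/DAST sample and no chart-review sample.

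**2. How much of the miss count item (1) could show.** Let r be the share of true cases that the team identifies, s1 the classifier's sensitivity in those cases, and s0 its sensitivity in the rest. None of these is in the documents.

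Visible share of misses = r(1 - s1) / [r(1 - s1) + (1 - r)(1 - s0)]

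- No correlation, r = 0.7, s1 = s0 = 0.80: 0.14 / (0.14 + 0.06) = 70%.
- Correlated, r = 0.7, s1 = 0.90, s0 = 0.30: 0.07 / (0.07 + 0.21) = 25%. Sensitivity among identified patients looks like 0.90, while overall sensitivity is 0.7 x 0.90 + 0.3 x 0.30 = 0.72.
- Over r = 0.5 to 0.9 with s1 = 0.90 and s0 = 0.10 to 0.30, the visible share runs from 0.05 / (0.05 + 0.45) = 10% to 0.09 / (0.09 + 0.07) = 56%.

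The item detects some misses. It detects a smaller share as the two sources become more correlated.

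**3. Whether the proportion screened and identified fills the gap.** Suppose identified means flagged. Take sensitivity and specificity at the 80% floor in the Scientific Review section.

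Flagged share = prevalence x sensitivity + (1 - prevalence) x (1 - specificity)

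- Prevalence 10% (assumed): 0.08 + 0.18 = 26%. If sensitivity fell to 60%, it would be 0.06 + 0.18 = 24%.
- Prevalence 25% (the upper figure in the same section): 0.20 + 0.15 = 35%. If sensitivity fell to 60%, it would be 0.15 + 0.15 = 30%.

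Misses double in both cases, while the flagged share moves by 2 or 5 percentage points. A large population-level fall would show, but the proportion does not separate missed patients from changes in false positives or case mix.

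**4. Gross scale.** Type and Number of Subjects expects about 57,800 patients. Spreading them evenly over 24 months is an assumption: 57,800 / 24 = 2,408 a month.

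Misses per month = 2,408 x prevalence x (1 - sensitivity)

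| Prevalence | Sensitivity 80% | Sensitivity 90% |
|---|---|---|
| 10% | 48 | 24 |
| 25% | 120 | 60 |

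The documents state sensitivity only as greater than 80%, so the 80% column is the high end.

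**5. Silent testing.** The figure of about 70 a month is one direction of disagreement: classifier positive, no consult. The reverse cell, positive under usual care and classifier negative, is not reported.

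**The case against.** The strongest reply is that item (1) is one measure among several and is not blind. Physician referral is a route to the Substance Use Intervention Team (Trial Setting and Participants), and care-team identification is nowhere defined as note text. A clinician who refers an unflagged patient adds to the count. A reader might infer that the count cannot rise, or that it rests on exactly the text the classifier reads. The documents support neither: the correlation is a probable inference, and the effect is an undercount.

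Second, classifier performance analyses, screening estimates for both methods and a withdrawal count are already planned. The classifier was also trained and tested on more than 35,000 hospitalizations screened with AUDIT and DAST. This stands, and it means the board is not left with nothing. But none of the planned items names what an unflagged patient would be checked against, and the retrospective testing does not describe the trial's own periods.

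Third, it is not certain that manual screening stops, because Clinical decision support and Potential Risks & Benefits disagree. The two passages must be reconciled. If screening does continue, the plan still does not say that its results will serve as the reference.

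Fourth, a reader might take the monthly figures as patients lost by the change. They are gross, with no manual-period comparator. The Scientific Review section says only a minority of hospital patients are screened, and silent testing found additional cases, so the net change could favour the classifier.

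Finally, any retrospective check is imperfect. AUDIT/DAST follows only a positive universal screen, toxicology tests are ordered on suspicion, and screening coverage differs between periods. These limits are real and have to be reported with the results.

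**Conclusion.** The point holds in a limited form. Item (1) measures recognised misses only. Neither it, the proportion screened and identified, nor the performance analyses as written can estimate the false-negative rate or the change from manual screening. This follows from the text. Its size does not: the visible share of 10-56% rests on assumed correlated detection, and the gross monthly counts rest on an even spread of patients, an assumed lower prevalence of 10% and the stated sensitivity floor. The direction, an undercount, requires only that some true cases are both unrecognised and unflagged. The point does not touch the primary endpoint, its model or the power calculation. It concerns what the board can conclude about missed patients, and it is worth correcting because the correction is cheap.

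**What to change.** 1. **Baseline analysis.** Make the planned baseline performance analysis a silent run of the frozen classifier on manual-period notes. Exclude documents that record the universal screen, AUDIT/DAST or the social-work or intervention-team work that followed; otherwise agreement is inflated. Cross-tabulate against AUDIT/DAST among patients actually screened, and report the screen-positive, classifier-negative cell to the board. State that verification is partial. Report the same reverse cell from the 2020 silent testing if it is available.
2. **After go-live.** Define care-team identification and its data source, and report item (1) with a denominator. Split by flag status the withdrawal count already planned and positive toxicology or alcohol laboratory results. To compare periods on the same footing, use the silent classifier's flag in the manual period. Treat ICD codes as supportive only, because they partly derive from clinician documentation.
3. **Text.** Reconcile Clinical decision support with Potential Risks & Benefits on whether the manual screen continues.

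The cost is analysis time on data already listed under Data Elements, with no added screening and no change to care. The markers give a relative missed-case rate, not an absolute one.
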